3.1 Overall Study Characteristics

Randomized, phase 2 study with cross-over design to assess the longitudinal impact of participation in the multi-disciplinary STAND clinic vs. receipt of usual standard of care on changes in key metabolic parameters, quality of life, and patient satisfaction among men receiving androgen deprivation therapy for prostate cancer. Standard-of-care therapy will consist of every 3-month visits comprised of review of medical history, toxicity assessment, and lifestyle modification counseling provided by individual health care provider, LHRH analog injections by trained oncology nurse. Patients in the usual care treatment arm will have unrestricted access to exercise, nutrition, and symptom management service upon patient request or as deemed necessary by health care provider. Men randomized to participation in the STAND clinic will have every 3 month visits with health care providers and LHRH analog injections, monthly self-directed educational “modules” covering the various aspects of hormone therapy as well as every 3-month individualized counseling provided by registered dietitian, exercise trainer, and symptom management service. At the end of 12 months of study participation, patients initially randomized to receive standard-of-care, will have the option of crossing-over to participate in the STAND clinic for the ensuing 12 months.

A non-randomized pilot cohort of patients receiving concurrent chemohormonal therapy will be enrolled in parallel to assess the feasibility of STAND clinic participation in this patient population.

3.2 Study Endpoints

3.2.1 Primary Endpoint

Randomized cohort: Mean percent change from baseline to 12 months in percentage body fat mass as measured by bioelectrical impedance analyzer (see Appendix 4).

Non-randomized chemohormonal cohort: Percentage of completed STAND clinic visits during the course of the 12 month STAND clinic participation.

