
Primary Objective
	
Randomized cohort: To compare the mean percent change from baseline to 12 months in percentage body fat mass among men with prostate cancer receiving androgen deprivation therapy randomized to participate in the “STAND” clinic vs. usual standard of care.
 
Non-randomized pilot cohort: To determine the feasibility of completing multi-disciplinary STAND clinic visits while undergoing concurrent chemohormonal therapy for prostate cancer.

Secondary Objectives
	
To compare the mean percent change from baseline to 12 months and patterns of change over time during participation in the STAND clinic vs. usual standard of care with respect to:
 
Metabolic Impact on Diabetes and Cardiovascular Risk Factors:
 
 - Fasting blood glucose - Fasting plasma insulin level - Insulin resistance as calculated by HOMA-IR - Hemoglobin A1c - Fasting lipids (total cholesterol, LDL, HDL, triglycerides) - Waist circumference - Body weight/body mass index - Exercise patterns as measured by validated questionnaire and home-based accelerometer assessment - Blood pressure

	
Bone Health:
 
 - Bone density as assessed by DXA scan - 25-(OH) vitamin D serum levels 
Quality of Life/Psychosocial Impact:
 
 - Depression as measured by PHQ-9 - Cognitive function as measured by the Attentional Functional Index - Overall quality of life as measured by SF-12 - Fatigue as measured by Lee Fatigue Scale - Erectile and urinary function as measured by EPIC-26 - Hot flash severity as measured by Hot Flash Related Daily Interference Scale 
Among men randomized to receive usual standard of care that cross-over to participate in the STAND clinic after month 12 of the study:
 
To measure the mean change from baseline at start of participation in the STAND clinic after 12 months of participation in:
 
 - Metabolic parameters including percentage body fat, fasting insulin/glucose, HOMA-IR, body weight/body mass index, waist circumference - Bone health - Quality of life 
Among men in the non-randomized pilot cohort:
 
 - To determine the mean change from baseline to 12 months during STAND clinic participation in the primary and secondary metabolic and quality of life parameters listed above.

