
Number of patients
	
80 patients with prostate cancer who are expected to receive at least 12 months of androgen deprivation therapy from the date of study enrollment will be enrolled.
 
A separate non-randomized patient cohort of 20 patients who are receiving concurrent chemohormonal therapy will be enrolled in parallel.

Duration of study
	
Patients randomized to participate in the STAND clinic will be followed for 12 months. Men initially randomized to the usual standard-of-care will have the option to cross-over onto participation in the STAND clinic after month 12, and will be followed in the STAND clinic for an additional 12 months or until 6 months following last dose of ADT, whichever is shorter. Patients enrolled in the non-randomized chemohormonal cohort will participate in STAND clinic for 12 months.

Study Assessments
	
In the STAND clinic treatment arm, patients will have every 3 month visits with a health care provider, along with monthly educational modules, and multi-disciplinary assessment and counseling by exercise, nutrition, and symptom management service on a rotating schedule. In the usual care treatment arm, patients will have every 3 month visits with their usual health care provider, and will have unrestricted access to exercise, nutrition, and symptom management services upon patient request or as deemed necessary by health care provider. In the non-randomized chemohormonal cohort, patients will have schedule modified as necessary to fit with chemotherapy dosing schedule but will have on average every 3 month counseling with physical therapist, nutrition, and symptom management.

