2.2 Study Objectives

2.2.1 Primary Objective

Randomized cohort: To compare the mean percent change from baseline to 12 months in percentage body fat mass among men with prostate cancer receiving androgen deprivation therapy randomized to participate in the “STAND” clinic vs. usual standard of care.

Non-randomized pilot cohort: To determine the feasibility of completing multi-disciplinary STAND clinic visits within context of concurrent chemohormonal therapy for prostate cancer.

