3.3 Study Schema

3.3.1 Primary Completion:

Study accrual is anticipated to be approximately 2 patients per month, leading to an accrual duration of approximately 40 months. Anticipated time from last patient enrolled to primary study completion and analysis of primary and secondary endpoints equals approximately 12 months, leading to the primary completion of study in approximately 52 months from first patient enrolled.

Study accrual of the 20 patient non-randomized chemohormonal cohort will be completed in parallel and is estimated to be approximately 0.8 patients/month, leading to an approximate 24 patient accrual period.

3.3.2 Study Completion:

The total study duration including follow up is estimated to be 5 years.

4. Study Population

80 evaluable patients with prostate cancer with concurrent or planned treatment with androgen deprivation therapy will be eligible for study participation. Patients must have initiated ADT within 6 months prior to day 1 of study entry, and the expected duration of ADT must be at least 12 months from study entry.

20 patients who are receiving or planning to receive concurrent chemohormonal therapy will be enrolled in a parallel non-randomized cohort, to establish the feasibility of completing STAND clinic visits in this patient population.

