4.1 Inclusion Criteria

- Histologic confirmation of adenocarcinoma of the prostate
- Receiving or planning to receive ADT with LHRH agonist or antagonist
- Expected duration of ADT at least 12 months from date of study consent
- Concurrent antiandrogen therapy allowed but not required
- First dose of LHRH agonist or antagonist no more than 6 months prior to date of study consent
- Prior/concurrent radiation allowed
- Other investigational agents in addition to LHRH agonist/antagonist are allowed (e.g. novel anti-androgens, androgen synthesis inhibitors)
- Prior androgen deprivation therapy allowed, provided there is documented evidence of testosterone recovery to > 150 ng/dL and greater than 12 months duration between last “effective” date of ADT and date of study consent
- **Randomized cohort only:**
 - No prior chemotherapy within 12 months of start date of study
 - No planned chemotherapy at least 12 months from study entry
- **Non-randomized pilot cohort:**
 - Concurrent chemotherapy (initiated within 3 months of study entry) or planned chemotherapy within 3 months of study entry
- ECOG performance status of 0 – 2
- Ability to sign written informed consent
- Willing to attend monthly clinic visits at UCSF

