9.2 Determination of Sample Size and Study Power

The sample size estimate is based upon the primary endpoint of the study, the mean percent change in percentage body fat from baseline to 12 months. Based on prior prospective longitudinal studies, it is estimated that men receiving ADT and standard-of-care physician counseling regarding expected toxicities will experience a mean 12% (sd = 17%) increase in percentage body fat after 12 months of ADT [13]. If men participating in the STAND clinic, with individualized exercise/nutrition counseling and longitudinal assessment, have, on average, no increase in percentage body fat mass after 12 months of hormone therapy, this would warrant further evaluation of a multi-disciplinary clinic in a larger randomized clinical trial with long-term endpoints of interest, including incidence of diabetes and potentially cardiovascular disease. An enrollment target of 32 evaluable patients per arm will provide power of 80% to detect an effect size of 0.71 in the difference in mean percent change from baseline to 12 months in percentage body fat mass between the two arms, using a two-sample t test and a two-tailed level of significance = 0.05. The total planned accrual is 40 patients per arm accounting for an inevaluable rate of 20%.

A sample size of 20 patients is chosen for the non-randomized chemohormonal cohort to establish the feasibility of a multi-disciplinary clinic in this patient population. The primary endpoint for this pilot cohort is the percentage of completed STAND clinic visits, with a target goal of 80%. A sample size of 20 patients (13 visits per patient; 260 visits in total) provides 17.5% precision to determine the percentage of completed visits at 95% confidence.

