9.5 Analysis Populations

The primary analysis for the randomized cohort will include all patients who have a body fat % measurement at baseline and at month 12 on study (± 2 weeks). If a patient comes off study prior to obtaining the end of month 12 body fat % measurement, they will not be included in the primary study analysis.

All patients enrolled in the chemohormonal non-randomized cohort who complete C1D1 visit will be included in the analysis of the primary endpoint, the percentage of completed visits in the STAND clinic.

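### The chemohormonal pilot asks about STAND visits during concurrent chemohormonal therapy, but its single 12-month percentage does not separate visits during chemotherapy from those before or after it, and the two can differ in either direction

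*Combined protocol and SAP*

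**What the plan says.** **Objective.** The synopsis states the pilot's primary objective as "To determine the feasibility of completing multi-disciplinary STAND clinic visits while undergoing concurrent chemohormonal therapy for prostate cancer". Section 2.2.1 places the same aim "within context of concurrent chemohormonal therapy for prostate cancer". Other places are looser. The opening of Section 4, for example, says the cohort is enrolled "to establish the feasibility of completing STAND clinic visits in this patient population", and the synopsis study design, 3.1, 7.3, 9.1 and 9.2 also refer to the population rather than to time on treatment.

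**Endpoint and follow-up.** Section 3.2.1 defines the endpoint as "Percentage of completed STAND clinic visits during the course of the 12 month STAND clinic participation". The synopsis fixes the period: "Patients enrolled in the non-randomized chemohormonal cohort will participate in STAND clinic for 12 months". Section 9.2 sets a goal of 80% and counts 13 visits per man, 260 in all. Section 9.3 alters the visit schedule if completion falls below 60% once 10 men have been enrolled for at least 6 months. Section 9.8.1 reports one point estimate with a 95% confidence interval.

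**Who is included.** Section 4.1 requires "Concurrent chemotherapy (initiated within 3 months of study entry) or planned chemotherapy within 3 months of study entry". It sets no minimum exposure. Section 9.5 adds: "All patients enrolled in the chemohormonal non-randomized cohort who complete C1D1 visit will be included in the analysis of the primary endpoint". A man who completes Day 1 and never starts chemotherapy is therefore counted in full.

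No section splits the percentage by whether chemotherapy was being given at the time of the visit.

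**The concern.** The synopsis objective concerns attendance during treatment. The endpoint mixes visits before, during and after chemotherapy, in proportions set by when each man enrolled relative to his first cycle and by how long his chemotherapy lasted. A pooled result near 80% would not show whether men kept to the clinic during chemotherapy, and a result below 80% would not show that they failed to. The 60% interim trigger has the same limitation. This is the cohort's only primary endpoint, so at stake is whether the pilot can answer its own stated question.

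**Working it through.** **The plan's own figure.** Section 9.2 gives 17.5% precision at 95% confidence. The half-width is 1.96 × √(p(1 − p)/n). With p = 0.80 and n = 20 it is 1.96 × √(0.16/20) = 0.175, which matches. With n = 260 independent visits it would be 0.049. The stated precision therefore treats the patient as the unit, and the same unit suits any split of the visits.

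**Inputs.** From the documents: 13 visits per man and the 80% goal (9.2), the 60% trigger and 6-month minimum (9.3), and planned chemotherapy up to 3 months after entry (4.1). My reading is that the 13 visits are Day 1 plus the ends of months 1 to 12. Not in the documents: chemotherapy length, and attendance on or off chemotherapy. Values used for these are assumptions.

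**Visits before chemotherapy.** For a month-3 start, Day 1 and months 1 and 2 come first. The month-3 visit coincides with the start and is counted as on chemotherapy. That leaves 3 of 13 visits (23%) before it.

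**On-chemotherapy completion compatible with a pooled 80%.** Let k be the number of visits during chemotherapy.

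pooled = (k × on + (13 − k) × off)/13

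Setting pooled = 0.80 (10.4 of 13 visits) gives on = (10.4 − (13 − k) × off)/k.

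| Case | k | off | on |
|---|---|---|---|
| All 13 visits during chemotherapy | 13 | none | 80% |
| Month 3 to month 12 | 10 | 100% | (10.4 − 3)/10 = 74% |
| Assumed shorter exposure | 6 | 95% | (10.4 − 6.65)/6 = 62.5% |
| Assumed shorter exposure | 5 | 95% | (10.4 − 7.60)/5 = 56% |
| Assumed shorter exposure | 4 | 95% | (10.4 − 8.55)/4 = 46% |

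The last two rows fall below the plan's own 60% trigger.

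**The opposite direction.** With k = 5, 90% completion on chemotherapy and 70% off it (assumed), pooled = (5 × 0.90 + 8 × 0.70)/13 = 10.1/13 = 78%. Here the pooled figure is 12 points below on-chemotherapy completion.

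**The interim look.** At 6 months a man has had about 7 visits (Day 1 to month 6). A month-3 starter still on chemotherapy at month 6 has 3 visits before it and 4 during it. If he keeps the first 3, his figure reaches 60% when (3 + 4 × on)/7 = 0.60, so on = (4.2 − 3)/4 = 30%. This is the latest start that 4.1 allows and describes one man's contribution. The trigger itself pools at least 10 men with mixed start dates.

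**The case against.** The strongest reply is that the pooled endpoint answers a legitimate question: can men given chemohormonal therapy complete a 12-month programme? Most descriptions of the pilot refer to the population, and participation is fixed at 12 months. Under that reading, endpoint and aim agree. This carries weight, and it is a reason to keep the all-visit percentage. It does not remove the conflict with the primary objective as the synopsis words it, which 2.2.1 only partly softens.

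A reader might infer that the pooled figure must overstate on-chemotherapy completion, perhaps by 16 to 31 points. Those values come from chosen inputs: 60% on and 90% off with k = 6 gives 76% pooled, 16 points higher; 50% on and 95% off with k = 4 gives 81%, 31 points higher. The documents support neither the chemotherapy length nor the attendance rates. Nor do they establish the direction. Section 7.5 matches visits to infusion appointments where possible, so attendance could be better during chemotherapy and fall afterwards.

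A reader might also infer that an on-chemotherapy percentage should replace the endpoint. That does not follow. Its denominator would depend on treatment received after entry. A man who stopped chemotherapy early and then left the clinic would contribute few visits, and his later missed visits would drop out. The rule in 9.5 avoids that selection.

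Finally, the 80% is a goal with no test or go/no-go rule, and the stated precision is 17.5 points either way. That limits the consequence.

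**Conclusion.** The mismatch between the stated objective and the single pooled percentage is real, and the plan has no analysis that resolves it. A pooled 80% is compatible with 74% completion on chemotherapy if treatment runs from month 3 to month 12 and all three earlier visits are kept. It is compatible with about 46% to 62.5% if only 4 to 6 visits fall during chemotherapy and 95% of the rest are kept. There is no gap if chemotherapy covers all 13 visits. At the interim, a man starting at month 3 can reach 60% with 30% attendance at his four on-chemotherapy visits. Except for the no-gap case, each figure rests on an assumed chemotherapy course and assumed attendance off it. The documents support the conclusion that the two percentages can differ either way; they do not support a fixed bias, or replacing the endpoint.

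**What to change.** Keep the all-visit percentage, in all men who complete Day 1, as the planned endpoint. Then:

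- **Section 9.8.1:** prespecify that completion is also reported separately for visits before, during and after each man's chemotherapy, using start and stop dates from treatment records. Give each a 95% confidence interval with the patient as the unit. Men who never start chemotherapy contribute to the all-visit figure only. State that the feasibility conclusion considers the on-chemotherapy figure alongside the pooled one.
- **Section 9.3:** make the same split available at the interim, and state that the review considers the on-chemotherapy percentage as well as the pooled one.
- **Synopsis and 2.2.1:** reconcile the wording of the objective with the population-based wording used elsewhere.

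The cost is SAP and protocol text plus the extraction of chemotherapy dates. Visits and treatment do not change. The on-chemotherapy interval will be somewhat wider, because each man contributes fewer visits and some men may contribute none. With 18 contributing men instead of 20, the half-width at 80% is 1.96 × √(0.16/18) = 18.5%, against 17.5%. Because its denominator depends on treatment received, the on-chemotherapy figure should be read beside the all-visit figure, not in place of it.

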3.2.2 Secondary Endpoints

Mean percent change from baseline to 12 months and patterns of change from baseline with respect to the following:

Metabolic Impact on Diabetes and Cardiovascular Disease Risk Factors:

- Fasting blood glucose
- Fasting plasma insulin level

- Insulin resistance as calculated by HOMA-IR
- Hemoglobin A1c
- Fasting lipids (total cholesterol, LDL, HDL, triglycerides)
- Waist circumference
- Body weight/body mass index
- Exercise patterns as measured by validated questionnaire and ambulatory accelerometer assessment (Appendices 2 and 5 respectively)
- Blood pressure

Bone Health:

- Bone density at the lumbar spine, femoral neck, and total hip as assessed by DXA scan among patients without bone metastases at the time of study entry
- Serum 25-(OH) vitamin D levels

Quality of Life/Psychosocial Impact:

- Depression as measured by PHQ-9
- Cognitive function as measured by Attentional Functional Index
- Overall quality of life as measured by SF-12
- Fatigue as measured by the Lee Fatigue Scale
- Erectile and urinary function as measured by EPIC-26
- Hot flash severity as measured by Hot Flash Related Daily Interference Scale

[figure not shown]
Patient Satisfaction:

- Patient satisfaction as measured by a validated questionnaire
- Patient insight and understanding of treatment and disease-related issues as measured by a self-administered assessment

3.2.3 Correlative Study Endpoints

- Association between inherited genetic polymorphisms of functional relevance near or within genes encoding proteins with roles in steroid hormone transport and androgen receptor signaling with changes in metabolic parameters among men treated with androgen deprivation therapy.
- Mean change from baseline in trabecular bone architecture as measured by trabecular bone number (TbN) and trabecular bone volume fraction (BV/TV) after 12 months of androgen deprivation therapy.
- Association between 2D:4D ratio with change in quality of life on androgen deprivation therapy.
- Association between 2D:4D ratio with baseline empathy score as measured by validated questionnaire.

3.3 Study Schema

3.3.1 Primary Completion:

Study accrual is anticipated to be approximately 2 patients per month, leading to an accrual duration of approximately 40 months. Anticipated time from last patient enrolled to primary study completion and analysis of primary and secondary endpoints equals approximately 12 months, leading to the primary completion of study in approximately 52 months from first patient enrolled.

Study accrual of the 20 patient non-randomized chemohormonal cohort will be completed in parallel and is estimated to be approximately 0.8 patients/month, leading to an approximate 24 patient accrual period.

3.3.2 Study Completion:

The total study duration including follow up is estimated to be 5 years.

4. Study Population

80 evaluable patients with prostate cancer with concurrent or planned treatment with androgen deprivation therapy will be eligible for study participation. Patients must have initiated ADT within 6 months prior to day 1 of study entry, and the expected duration of ADT must be at least 12 months from study entry.

20 patients who are receiving or planning to receive concurrent chemohormonal therapy will be enrolled in a parallel non-randomized cohort, to establish the feasibility of completing STAND clinic visits in this patient population.

4.1 Inclusion Criteria

- Histologic confirmation of adenocarcinoma of the prostate
- Receiving or planning to receive ADT with LHRH agonist or antagonist
- Expected duration of ADT at least 12 months from date of study consent
- Concurrent antiandrogen therapy allowed but not required
- First dose of LHRH agonist or antagonist no more than 6 months prior to date of study consent
- Prior/concurrent radiation allowed
- Other investigational agents in addition to LHRH agonist/antagonist are allowed (e.g. novel anti-androgens, androgen synthesis inhibitors)
- Prior androgen deprivation therapy allowed, provided there is documented evidence of testosterone recovery to > 150 ng/dL and greater than 12 months duration between last “effective” date of ADT and date of study consent
- **Randomized cohort only:**
 - No prior chemotherapy within 12 months of start date of study
 - No planned chemotherapy at least 12 months from study entry
- **Non-randomized pilot cohort:**
 - Concurrent chemotherapy (initiated within 3 months of study entry) or planned chemotherapy within 3 months of study entry
- ECOG performance status of 0 – 2
- Ability to sign written informed consent
- Willing to attend monthly clinic visits at UCSF

